Endpoint	The primary outcome will be the percentage of swallows with aspiration and/or penetration for cold milk compared with room temp milk (a total of 15 swallows will be assessed by VFSS and FEES). Based on our preliminary results, we expect to find a significant decrease in penetration and aspiration during the initial cold swallows (5 swallows). We expect this improvement to be sustained on the subsequent cold swallows (10 swallows) following the 15-minute cold liquid feeding. A decrease of 30% in penetration and/or aspiration with cold milk will be considered significant. Similarly, a 30% improvement of feeding coordination as assessed by nFant device will be considered significant.
	2. Evaluate the safety of feeding cold milk in preterm infants. We will evaluate whether cold milk will cause hypothermia (assessed by measuring Axillary temperatures), change in vital signs (respiratory rate, heart rate, and oxygen saturation) as well as change in mesenteric blood flow indices (assessed by abdominal ultrasound) These changes with cold milk feeding will be expressed as % change compared to base line (room temp milk).
Study Duration	2 years
Participant Duration	The subjects will participate in the study for approximately 48 hours during their NICU hospital stay
Population	Preterm Infants less than 34 weeks gestation admitted to NYU- Langone Long Island Hospital NICU. (n=42)
Study Sites	NYU- Langone Long Island Hospital
Number of participants	42

1. Introduction, Background Information and Scientific Rationale

Approximately half a million preterm infants are born every year in the USA.^{1,2} It is estimated that 30-70% of very low birth weight (VLBW) preterm infants will be diagnosed with swallowing dysfunction (dysphagia), with an inverse relationship between the severity of dysphagia and gestational age (GA).³⁻⁶ Although the pathophysiology of dysphagia is multifactorial,^{4,7-9} the discoordination between swallowing and breathing is the most prevalent cause of dysphagia in preterm infants,¹⁰ which often leads to airway compromise in the form of laryngeal penetration and/or tracheal aspiration into the lungs.^{7,11} Chronic airway compromise results in a persistent inflammatory state, with disease progression to chronic lung injury and *bronchopulmonary dysplasia (BPD)* that can be devastating for already fragile and developmentally immature lungs in preterm infants.^{4,7}

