- The axillary temperature will be measured immediately prior to and after each feeding condition. It will also be measured at 10, and 30 minutes after the CS feed, at the same time the gastric content temperatures are taken. Infants' vital signs will be recorded (blood pressure, respiratory rate, heart rate, and oxygen saturation), as well as evidence of bronchospasm, lethargy, respiratory distress, apnea, tachypnea, cyanosis, bradycardia, or tachycardia.
- Doppler ultrasound (Sonosite Edge Ultrasound system, Sonosite, Inc, WA) will be used to measure
 intestinal blood flow indices including the superior mesenteric artery flow (SMA), peak systolic velocity,
 SMA mean velocity, SMA end-diastolic velocity, resistive index, pulsatility index, portal vein volumetric
 blood flow, as well as heart rate and mean arterial blood pressure. Intestinal blood flow monitoring via
 Doppler ultrasound will be performed 6 times for each participant, performed one hour before and at 30 and
 60 minutes after both bedside feeding conditions (RTS and CS). Measurements will be taken at the bedside
 in the supine position.
- Step 2 (done 24-48 hours after step 1):
 - Infants will be transported to the radiology suite and undergo VFSS and or FEES, as ordered by the treating
 medical team (Figure1: the blue boxes indicate procedures done for research purpose only. None of the
 research procedures are experimental and are approved tests for neonates including VFSS, FEES, nfant
 test and abdominal ultrasound).
 - Routine procedure for VFSS or FEES will be followed as ordered by the medical team. This procedure is part of the routine clinical care and not considered part of the research study.
 - If no dysfunction is noted, the procedure will end, and the child will no longer be eligible for further participation in this research study. If dysfunction (penetration/aspiration) either on the VFSS or FEES study is noted, the child will be eligible to participate in the next phase of the study.
 - Immediately following the initial VFSS-FEES assessment, the infants will remain in the same seated position with the FEES scope in place. While keeping all variables from the standard VFSS-FEES the same, the infant will be fed cold barium (4-9°C) using the same nipple. A total of 5 swallows will be visualized using VFSS and FEES, labeled "Cold Swallows-1 (CS1)." These 5 swallows assessment are done for the research purpose only.

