Statistical Analysis and Estimated Sample Size: To evaluate whether cold liquid will improve aspiration and penetration, event rates during CS compared to RTS, as well as corresponding 95% confidence intervals, will be computed. Aspiration and Penetration variables will be assessed for normality using histograms and the Kolmogorov-Smirnov (K-S) test. Wilcoxon Signed-Rank test will be used to evaluate the specific aim 1, i.e., compare changes in aspiration and penetration between RTS and CS. Aspiration and penetration will be evaluated using different methods (FEES and VFSS). Power and Sample Size: Our preliminary data showed a mean change of 44 and 36% in aspiration and penetration, respectively. For power computation, we conservatively assumed an average change of 30% and a common standard deviation of 25 in both aspiration and penetration. We simulated data using a two-sided Wilcoxon Signed-Rank Test (the non-parametric equivalent of the paired t-test) with alpha=0.05 significance level and a pre-post correlation of 0.20, which revealed that a sample size of N=25 subjects would provide us more than 95% power to detect a large effect size both in aspiration and penetration. These simulation results are based on 10000 Monte Carlo samples. Assuming a conservative estimate that 60% of infants with clinical dysphagia will have a positive VFSS or FEES test, we expect that we will need to enroll 42 subjects to have 30 subjects with a positive dysphagia test. NYU- Langone Long Island Hospital Hospital NICU is a Regional Perinatal Center (one of 17 NICUs in the state of New York designated to provide the highest level of care to neonates in NY State). The average number of VLBW infants admitted is 90-100/year and at least 40-45 infants/year will have clinical dysphagia referred for VFSS-FEES testing (3-4 patients/month). Therefore, we are confident that we will have sufficient sample size over the 2-year grant period to conduct the proposed aims.

2: Evaluate the safety of feeding cold milk in preterm infants.

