Our preliminary data (REF) showed a mean change of 44 and 36% in aspiration and penetration, respectively. For power computation, we conservatively assumed an average change of 30% and a common standard deviation of 25 in both aspiration and penetration. We simulated data using a two-sided Wilcoxon Signed-Rank Test (the non-parametric equivalent of the paired t-test) with alpha=0.05 significance level and a pre-post correlation of 0.20, which revealed that a sample size of N=25 subjects would provide us more than 95% power to detect a large effect size both in aspiration and penetration. These simulation results are based on 10000 Monte Carlo samples. Assuming a conservative estimate that 60% of infants with clinical dysphagia will have a positive VFSS or FEES test, we expect that we will need to enroll 42 subjects to have 30 subjects with a positive dysphagia test.

Informed Consent Process

Informed consent is a process that is initiated prior to the individual's agreeing to participate in the study and continues throughout the individual's study participation. Extensive discussion of risks and possible benefits of participation will be provided to the infants' parents. Consent forms will be IRB-approved and the parents (defined as either the mom or dad if they are legally married) will be asked to read and review the document. The study investigators will explain the research study to the parents and answer any questions that may arise. All participants will receive a verbal explanation in terms suited to their comprehension of the purposes, procedures, and potential risks of the study and of their rights as research participants. Parents will have the opportunity to carefully review the written consent form and ask questions prior to signing. The parents should have the opportunity to discuss the study with their surrogates or think about it prior to agreeing to participate. The parents will sign the informed consent document prior to any procedures being done specifically for the study. The parents may withdraw consent at any time throughout the course of the study. A copy of the signed informed consent document will be given to the parents for their records. The rights and welfare of the participants will be protected by emphasizing to them that the quality of their medical care will not be adversely affected if they decline to participate in this study.

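### Aim 1 is read on both FEES and VFSS with no deciding instrument; if either result may carry the claim, the two-sided false-positive rate is about 7-10% on one outcome

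*Combined protocol and SAP*

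**What the plan says.** The Endpoint row of the synopsis gives one outcome: "The primary outcome will be the percentage of swallows with aspiration and/or penetration for cold milk compared with room temp milk", with the note that "a total of 15 swallows will be assessed by VFSS and FEES". It adds that a 30% decrease will count as significant, without naming an instrument.

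Under Statistical Considerations, the "Wilcoxon Signed-Rank test will be used to evaluate the specific aim 1, i.e., compare changes in aspiration and penetration between RTS and CS", and the next sentence is "Aspiration and penetration will be evaluated using different methods (FEES and VFSS"). Here aspiration and penetration appear as two variables rather than one composite. The alpha of 0.05, two-sided, appears only in the power calculation. That calculation, repeated in Section 6, concludes that "a sample size of N=25 subjects would provide us more than 95% power to detect a large effect size both in aspiration and penetration".

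In Section 4, Step 2, the clinical study is not fixed to one instrument: "Infants will be transported to the radiology suite and undergo VFSS and or FEES, as ordered by the treating" medical team. The first cold swallows are then seen on both: "A total of 5 swallows will be visualized using VFSS and FEES". The design contains an either/or rule, "If dysfunction (penetration/aspiration) either on the VFSS or FEES study is noted, the child will be eligible", but it governs entry to the next phase. The sample-size text also counts a positive result on either instrument, but only to forecast how many infants will qualify.

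**The concern.** The two instruments can disagree on the same infants, and the plan has no rule for that case. The choice of reading would then be made after the data are seen, and 0.05 would no longer describe the error rate of the claim. The problem would remain if a single swallow variable were fixed and if room-temperature and cold swallows were always compared on the same instrument. It grows if aspiration and penetration are tested separately.

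The choice of reading also affects sample size. An instrument-specific paired test can use only infants whose routine room-temperature study included that instrument.

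The stakes are practical. Section 4 says that, if efficacy and safety are shown, clinicians could use cold milk without repeating the study's measurements in each child.

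**Working it through.** **Inputs from the plan.** Mean change 30, SD 25, pre-post correlation 0.20, two-sided alpha 0.05, N=25 (Statistical Considerations and Section 6). There are two instruments, and one outcome (synopsis) or two (statistical section).

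**Assumed inputs.** The documents do not give the correlation between the tests; the range used is 0 to 0.9. They do not give the number of infants with each instrument at room temperature; the range used is 12 to 25.

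**Step 1: the plan's own power.** SD of the paired difference = 25 × √(2 × (1 − 0.20)) = 31.6. Standardised effect = 30/31.6 = 0.95. Normal approximation at N=25: Φ(0.949 × √25 − 1.96) = Φ(2.78) = 0.997. Simulating the exact Wilcoxon signed-rank test (10,000 samples) gives 0.994. The stated figure of more than 95% is reproduced.

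**Step 2: chance of at least one p<0.05 when there is no effect.** For k independent tests the rate is 1 − (1 − 0.05)^k:

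- two tests: 1 − 0.95² = 0.0975;
- four tests: 1 − 0.95⁴ = 0.185.

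For correlated tests, one million multivariate normal draws with equal correlation give the rates below. Benefit only means significant in favour of cold milk; a single test has a rate of 2.5%.

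| Correlation | Two tests, two-sided | Two tests, benefit only | Four tests, two-sided | Four tests, benefit only |
|---|---|---|---|---|
| 0 | 9.8% | 4.9% | 18.5% | 9.6% |
| 0.5 | 9.1% | 4.5% | 15.6% | 7.8% |
| 0.8 | 7.8% | 3.9% | 11.4% | 5.7% |
| 0.9 | 7.0% | 3.5% | 9.4% | 4.7% |

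Running the Wilcoxon test itself at n=25 and correlation 0.5 gives 9.0% and 15.1%. Letting the correlation differ between instruments (0.5 to 0.9) and between outcomes (0 to 0.5) gives 12.5% to 17.4% for four tests, inside the same range.

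The same cold swallows are seen on both instruments, which points to the higher correlations. If some infants have only one instrument at room temperature, the two tests use partly different infants, and the rate moves back towards 9.75%.

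**Step 3: power of one per-instrument test with fewer infants.** Inputs as in Step 1, alpha 0.05:

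| Infants with that instrument at room temperature | Power |
|---|---|
| 25 | 0.994 |
| 18 | 0.959 |
| 15 | 0.913 |
| 12 | 0.809 |

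About 18 infants are needed to keep 95%. The plan's own 60% positive rate gives 0.60 × 42 = 25.2 positive infants in all, so there is little reserve.

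**Step 4: cost of adjusting.** At N=25, power is 0.984 at alpha 0.025 (two tests) and 0.966 at alpha 0.0125 (four tests). These are the strictest steps of a Holm procedure.

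**The case against.** The strongest reply is that the plan is silent rather than permissive. The disputed sentence describes how swallows are assessed. It does not say that either instrument's p-value is enough. The synopsis gives one composite percentage assessed by both instruments, and one combined value per infant, hence one test, is an equally open reading. This stands. A reader might infer that the plan authorises reporting whichever instrument is significant, but no text says so. The defect is a missing rule, and the rates in the working apply only if either reading may carry the claim.

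A reader might also infer that the two instruments alone raise the error rate to about 16%. They cannot: two tests at 0.05 are bounded by 10%. The higher figure needs aspiration and penetration as separate routes to success, which the statistical section allows but the synopsis outcome does not clearly support. It also needs an assumed correlation near 0.5.

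The 30% criterion could remove the problem. If it is an extra requirement of 30 percentage points, then with a standard error of 31.6/√25 = 6.3 it lies about 4.7 standard errors from zero, and chance success on either instrument is negligible. The synopsis does not say whether the 30% is absolute or relative, or whether it adds to p<0.05 or replaces it. The objection therefore shows a further ambiguity but does not settle the matter.

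Finally, a reader might infer that each per-instrument test must fall short of 25 infants. Section 4 often describes VFSS and FEES as done together, so a shortfall is possible but not shown.

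**Conclusion.** The concern holds as a gap in the decision rule. Aim 1 is evaluated on two instruments, with no deciding instrument, no combined reading for analysis and no adjustment. That full alpha applies to each test is inferred from the power paragraph and the absence of any split.

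The resulting error rates, about 7-10% for one outcome and about 9-19% for two, are conditional on either reading being allowed to decide and on p<0.05 being the only criterion. The separate possibility of a smaller N matters for the stated power only if fewer than about 18 infants have the instrument in question at room temperature.

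The study is described as seeking preliminary evidence, which lowers the stakes. A test reported at 0.05 still needs one rule fixed in advance. This should be changed, but it does not undermine the design.

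**What to change.** Replace the sentence on FEES and VFSS under Statistical Considerations with wording to this effect:

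> The Aim 1 decision rests on one Wilcoxon signed-rank test at two-sided 0.05 of the primary outcome in the synopsis (the share of swallows showing penetration, aspiration or both). Each infant contributes one value per condition, read on the same instrument in both: VFSS where it was part of the routine room-temperature study, otherwise FEES. Separate aspiration, penetration, FEES-only and VFSS-only analyses are supportive.

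Putting VFSS first follows the group's pilot, which Section 1 says was assessed by VFSS. A combined reading defined in advance would serve equally well.

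If more than one test is meant to support a claim, apply Holm across all of them (up to four, not only across the two instruments) and report the number of infants in each. Attach the power statement of more than 95% to the single primary test only. State whether the 30% criterion is absolute or relative, and whether it is additional to p<0.05.

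The cost is a paragraph of text, with no new data, infants or procedures. The downside is that a result seen only on the non-primary instrument, or only on one component, can no longer be claimed as confirmatory.

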Radiation Exposure - For this study, we aim to visualize 15 swallows, which will take approximately 18 seconds. Compared to the typical range of radiation time of 90-180 seconds in routine VFSS. The radiation exposure related to this research equals 10-20% of what an infant would be exposed to during a typical routine VFSS.

Radiation Exposure Prevention – Our study design will include various radiation sparing techniques: 1) Commination, which restricts the x-rays to a smaller area on the subject; 2) Pulsed fluoroscopy, which takes 30 frames/second, instead of the continuous fluoroscopy of 60 frames/second; 3) The radiologist will utilize intermittent fluoroscopy to turn the radiation on only at the time of swallowing; 4) A lead shield will be placed on the subjects' lap to protect reproductive organs from radiation scatter.

Known Potential Benefits

The subjects may or may not personally benefit from being in this study. The results of this research (the safety and effectiveness of cold milk for each subject) will be disclosed to the medical team for further consideration. If the

results confirm safety and efficacy for that infant, the medical team can consider using cold milk to treat the infant's dysphagia which can be a significant benefit to the subject.

3. Objectives

The first objective is to identify preliminary evidence for the efficacy of feeding full oral cold milk for dysphagia management in preterm infants. We hypothesize that oral feeding of cold milk in preterm infants with dysphagia will improve suck/swallow/breathe coordination and decrease penetration/aspiration to the airway. Our second objective is to confirm the safety of this practice. We hypothesize that cold milk intervention will have no adverse effects on intestinal blood flow as assessed by Doppler Ultrasound. These objectives are significant because there is a critical need to identify effective and safe evidence-based treatment options for dysphagia management in preterm infants.

4. Study Design

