This will be a prospective study, with each infant serving as their own control. All study subjects will meet the inclusion/exclusion criteria listed in Section 5 of this proposal and informed consent will be obtained. The subject will be considered for the study if the medical team diagnosed the infant with clinical dysphagia and decided to obtain Video Fluoroscopic Swallow Study (VFSS), or Fiberoptic Endoscopic Evaluation of Swallowing [FEES) or both to help manage the dysphagia (such as delay oral feeding till the child is more mature or use feeds thickeners). The VFSS and FEES are not a requirement for step 1 however abnormal VFSS and FEES are requirement for step 2.

The following study procedures will be done before the routine VFSS/FEES testing ordered by the medical team:

Study Protocol Timeline

• Step 1 (bedside procedures):

- We will evaluate the infant's sucking, swallowing, and breathing patterns using a non-invasive FDA approved equipment (nFant® Feeding Solution). This device is in clinical use for several years and routinely used in several NICUs. The nFant has a wireless sensor within the nipple to assess sucking and swallowing coordination during feeding. This machine is not routinely used in NYU- Langone Long Island Hospital NICU because of costs but will be available only for infants enrolled in this research study. The nfant assessments will be performed by the research team under two separate feeding conditions, standard room temperature (RTS) and cold temperature (CS, at 4-9°C) of milk/formula for an entire feeding (15-20 minutes). The two feedings will be done on the same day but may not necessarily be two consecutive feedings (depending on the baby's eagerness to feed orally). The order of each condition will be randomized to control for fatigue. Inter- and intra-rater reliability measures will be calculated. The nfant assessments will include the following measurements:
 - peak amplitude the displacement of the nipple during compression phase normalized from a calibrated 0% to 100%;
 - duration how long or drawn out sucking events are from onset to end in seconds;

- frequency the rate at which consecutive suck events are occurring in Hertz;
- > suck bursts number of sucks per burst, duration and number of bursts, and active time spent sucking;
- > suck smoothness the number of velocity changes in a nipple amplitude trace during a suck.

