Axillary temperatures, as well as mesenteric blood flow indices, will be compared between the CS and RTS feeds. A Two One-Sided Test (TOST) will be used to evaluate whether the body temperature and blood flow indices are equivalent before and after the cold liquid swallow. Equivalence will be determined if the 90% confidence interval of pre-post change is contained within the predefined margin of ± 0.5 . *Power and sample size:* The study subjects are the same subjects enrolled in Aim 1 (n=42). We have simulated data assuming a margin of equivalence from - 0.5° C to 0.5° C, significance level 0.05, TOST and 10000 Monte Carlo samples. With the planned sample size for aim 1 (N=42), we will have sufficient power (>80%) to detect equivalence when the margin of equivalence is from - 0.5° C to 0.5° C and the actual mean difference is zero.

5. Study Enrollment

Inclusion Criteria

 Viable preterm infants less than 34 weeks gestation), 2) admitted to NYU- Langone Long Island Hospital NICU, 3) PMA > 35 weeks at the time of the study, 4) receiving no or minimum respiratory support (<2 lit/min low-flow nasal cannula), 5) tolerating at least 50% of their enteral feeding orally and 6) having symptoms of swallowing dysfunction during oral feeding (clinical dysphagia). 7) referred by the medical team for VFSS and/or FEES assessments.

Exclusion Criteria

Exclusion criteria include children with other comorbidities, such as IUGR, upper airway anomalies, brain injury, neuromuscular disease, or life-threatening congenital disease.

Total Number of Participants and Sites

We will need 42 subjects over a 2 years period.

Vulnerable Subjects

Our population will include children by nature of the study objectives.

The study has potentially greater than minimal risk, but there is possible direct benefit to the individual subject. Although previous studies as well as our preliminary study didn't show any evidence of cold stress in response to cold milk feeding, it is a potential risk. In addition there will be minor increase in radiation exposure as described previously. Currently there is no effective treatment for dysphagia in preterm infants. The results of this research (the safety and effectiveness of cold milk for each subject) will be disclosed to the medical team. If the results confirm safety and efficacy for that infant, the medical team can consider using cold milk to treat the infant's dysphagia which can be a significant benefit to the subject.

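### The Aim 2 equivalence test is worded as a before-after change around the cold feed, not as the announced cold versus room-temperature contrast; this matters mainly for Doppler flow

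*Combined protocol and SAP*

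**What the plan says.** The safety part of Statistical Considerations (Section 4, Aim 2) opens with a between-feed comparison: "Axillary temperatures, as well as mesenteric blood flow indices, will be compared between the CS and RTS feeds". The next sentence introduces the TOST, to evaluate "whether the body temperature and blood flow indices are equivalent before and after the cold liquid swallow". The decision rule follows: "Equivalence will be determined if the 90% confidence interval of pre-post change is contained within the predefined margin of" ±0.5. No other test, interval or margin for these outcomes appears in the document.

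Three other places bear on what the contrast is meant to be.

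- The Endpoint entry of the synopsis says of the same outcomes: "These changes with cold milk feeding will be expressed as % change compared to base line (room temp milk". No test is attached.
- The Aim 1 power statement, whose comparison is RTS against CS, refers to "alpha=0.05 significance level and a pre-post correlation of 0.20".
- Section 4, Step 1, says of the bedside feeds: "The two feedings will be done on the same day", and "The order of each condition will be randomized to control for fatigue".

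Step 1 also fixes the measurements. Doppler is done an hour before each of the two feeds and again 30 and 60 minutes after it, six times per infant. Axillary temperature is taken just before and just after each feed, with further readings at 10 and 30 minutes after the cold feed only.

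Flow is the stated safety hypothesis in Section 3: "We hypothesize that cold milk intervention will have no adverse effects on intestinal blood flow as assessed by Doppler Ultrasound".

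**The concern.** As worded, the TOST uses the cold feed alone. The change in a flow index from before to after that feed is the sum of two parts: what any feed does (feeding, handling, elapsed time) and what the temperature of the milk adds. The safety hypothesis concerns the second part, and the test sees only the sum.

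The error can go either way. A feed effect opposite in sign to the cold effect can bring the sum inside the margin although CS and RTS differ by more than the margin. A feed effect alone can push the sum towards or past the margin although CS and RTS do not differ. The RTS feed, with its own Doppler series in the same infant on the same day, is the control that separates the two parts, and the rule as worded does not use it.

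Axillary temperature is different. Whether an infant is colder after a cold feed is a safety question in its own right, and the before-after change answers it.

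**Working it through.** **1. The wording.** Two readings of the pre-post change are possible.

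| Reading | For | Against |
|---|---|---|
| Post minus pre around the cold feed | The TOST sentence says so; Step 1 gives each feed its own pre and post measurements | The preceding sentence announces CS versus RTS |
| RTS to CS | That preceding sentence; the synopsis takes room-temperature milk as baseline; Aim 1 uses pre-post for its RTS-CS comparison | The TOST sentence names the cold swallow; with randomised order, RTS is not always first |

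The first reading is the natural one. Under the second, the text still does not say whether post-feed values or changes are compared, or at which time.

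**2. The plan's own figure.** Aim 2 states more than 80% power with N=42, margin ±0.5°C, level 0.05 and true difference zero. No SD is given, so this can be neither confirmed nor refuted. Inverting the TOST power, it holds if the SD of the analysed difference is at most about 1.09°C. The figure does not show which contrast was simulated.

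**3. Whether the contrast matters for Doppler.** The documents give no SD, correlation, feed effect or usable Doppler margin for Aim 2. The inputs below are therefore assumptions, in units of the margin M.

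- n = 42 (Aim 2); SD of change in each feed = M; the two changes uncorrelated; balanced order.
- True cold effect (CS minus RTS) = -1.25M, so the feeds are not equivalent; feed effect = +0.5M.
- The test passes if estimate ± t × SE lies within ±M.

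*Before-after, cold feed only.*
- True mean = -1.25M + 0.5M = -0.75M.
- SE = M/√42 = 0.154M; t (41 df) = 1.683; half-width = 0.260M.
- To pass, the estimate must exceed -1M + 0.260M = -0.740M.
- z = (-0.740 + 0.75)/0.154 = 0.06, so the pass probability is about 0.475. Allowing for the estimated SD gives **48%**.

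*CS minus RTS, difference of changes with a period term.*
- True mean = -1.25M; SD = √2 × M = 1.414M; SE = 0.218M; t (40 df) = 1.684; half-width = 0.367M.
- To pass, the estimate must exceed -0.633M.
- z = (-0.633 + 1.25)/0.218 = 2.83, so the pass probability is about 0.002. Allowing for the estimated SD gives **0.3%**.

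**4. Dependence on the feed effect.** Same inputs, before-after test, cold effect -1.25M:

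| Feed effect | Declares equivalence |
|---|---|
| -0.5M (same direction as cold) | 0% |
| 0 | 0.1% |
| +0.25M | 5% |
| +0.5M | 48% |

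**5. The opposite error.** With cold effect zero and feed effect ±1.0M, the before-after test passes 5% of the time and CS minus RTS 99.6%. With feed effect ±0.5M, the before-after test still passes 94%.

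**6. Price of the contrast.** Take both effects as zero, SD of change 1.5M and uncorrelated changes.
- Before-after: SE = 1.5M/√42 = 0.231M. The estimate must lie within ±0.61M, and the test passes **99%** of the time.
- CS minus RTS: the variance doubles and SE = 0.327M. The estimate must lie within ±0.45M, and the test passes **83%** of the time.
- With a correlation of 0.5 between the changes, both pass about 99%.

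**The case against.** The strongest reply is that the authors mean RTS to CS throughout. The between-feed sentence comes immediately before the TOST, the synopsis treats room-temperature milk as baseline for these very outcomes, and Aim 1 already uses pre-post in that sense. This has weight. A reader might infer that the announced comparison has no decision rule at all; the documents do not support going that far, because on this reading the TOST is the rule. What remains is that the TOST sentence and the randomised order point the other way, so the contrast still has to be defined.

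Secondly, the false pass needs an opposing feed effect of some size, and no document gives one. That is correct. The illustration shows that the two contrasts can disagree, not how likely that is here.

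Thirdly, the before-after test is sound for temperature. That stands too: it is a valid check on net cooling, and individual hypothermia is handled as an adverse event in the Safety Monitoring Plan.

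Finally, CS minus RTS rests on an assumption of its own. The feeds share a day and may be consecutive, no washout is stated, and the second feed's baseline Doppler could carry residual effect of the first. A period term does not remove carry-over. This limits the remedy and should be stated, but it does not favour a test that omits the control feed.

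**Conclusion.** The point holds as one of an unclear and, on its natural reading, mismatched contrast. It bears mainly on Doppler flow. A cold-feed-only change does not isolate the effect of milk temperature, which is what the flow hypothesis needs. Under the stated assumptions the two contrasts give 48% against 0.3% false equivalence. With no feed effect, or one in the same direction as cold, the before-after rule does not wrongly pass to any relevant degree (at most 0.3% for SDs of 0.5M to 1.5M).

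A reader might infer that the trial is bound to declare cold milk safe wrongly, or that the temperature test is invalid. Neither follows: the documents are silent on the feed effect, and the temperature test answers a legitimate question. The conclusion about wording needs none of the assumed inputs. The percentages need all of them, and the advantage of CS minus RTS also needs no carry-over between the feeds. This should be corrected before analysis; it does not compromise the data being collected.

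**What to change.** Reconcile the synopsis Endpoint entry with the Aim 2 text and state the contrast explicitly.

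- **Doppler.** Apply the TOST to the within-infant CS-minus-RTS contrast, for example (CS post minus pre) minus (RTS post minus pre), allowing for feed order, at a time point named in advance. A baseline-adjusted comparison would also serve. State that this assumes no carry-over between the two same-day feeds.
- **Axillary temperature.** Keep the before-after test on the cold feed as a check on net cooling and name the reading that decides it. Add CS minus RTS immediately after the feed as a separate result, since the later readings follow only the cold feed. The two answer different questions, so do not require both to pass.

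Everything needed is already in the Step 1 schedule. The costs are a choice of time point by the sponsor and some power. If feeding has no effect and the changes are uncorrelated, the contrast has twice the variance (83% against 99% at SD 1.5M). For temperature, 80% power then needs a per-feed SD of change of at most 1.09/√2 = 0.77°C, against 1.09°C for the before-after test.

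A separate matter must be settled first on either contrast: the ±0.5 margin has no unit for the flow indices, so the Doppler TOST cannot be applied until each index tested has a justified margin in its own unit.
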